TITLE:	Adductor Canal Catheter Effectiveness and Safety Study (ACCESS)
PRIMARY OBJECTIVE:	Compare the effect of usual care with an adductor canal catheter (ACC) containing ropivacaine to the effect of usual care without an ACC on the second-postoperative-day pain levels among patients undergoing elective primary unilateral total knee arthroplasty (TKA)
SECONDARY OBJECTIVES:	
Among a sample of patients undergoing elective primary unilateral TKA who receive peri-articular anesthetic injections:
 
1) To compare the overall two-week levels of postoperative pain between those participants randomized to ACCs containing ropivacaine and those participants randomized to usual care without an ACC2) To compare the use of opioid medications (in mean total morphine milligram equivalents) between those participants randomized to ACCs containing ropivacaine and those participants randomized to usual care without an ACC over the two-week postoperative period3) To describe the incidence of complications related to ACC placement including infection, displacement, ACC-related clinic or emergency department (ED) visits4) To conduct exploratory analyses to identify candidate predictors of differential response to the ACC
DESIGN:	Randomized, open-label, two-arm, parallel-comparison noninferiority trial
POPULATION:	Adults aged ≥ 18 years intending to undergo elective primary unilateral TKA at the KPNC San Leandro Medical Center
INTERVENTION:	Participants will be randomized to one of two treatment arms: 
▪ Adductor canal catheter placement in the pre-operative area immediately prior to TKA surgery OR▪ No adductor canal catheter placement
DURATION:	The intervention phase will occur between randomization and three days postoperatively (or until the ACC is removed by the participant or the ACC falls out spontaneously among ACC-randomized participants); the primary outcome will be measured on postoperative day 2, secondary pain and medication outcomes will be collected for two weeks postoperatively and the electronic medical record (EMR) will be examined for evidence of adverse events at 3 months postoperatively
SAMPLE SIZE:	132 participants randomized using balanced allocation to the two study arms

0.1 ACRONYMS USED IN THIS PROTOCOL

ACB = Adductor Canal Block

ACC = Adductor Canal Catheter

ACCESS = Adductor Canal Catheter Effectiveness and Safety Study

AE = Adverse Event

DOA = Division of Research

DSM = Data and Safety Monitor

ED = Emergency Department

EMR = Electronic Medical Record (KPNC HealthConnect)

ERAS = Enhanced Recovery After Surgery

ICH = International Council for Harmonization

IDE = Investigational Device Exemption

IND = Investigational New Drug

IRB = Institutional Review Board

KPNC = Kaiser Permanente, Northern California

MCID = Minimum Clinically Important Difference

NRS = Numerical Rating Scale

NSAID = Non-Steroidal Anti-Inflammatory Drug

PAI = Peri-Articular Injection

PHI = Protected Health Information

PROMIS = Patient-Reported Outcomes Measurement Information System

RCT = Randomized Clinical Trial

SAE = Serious Adverse Event

SLN = San Leandro (KPNC Medical Center)

TKA = Total Knee Arthroplasty

UP = Unanticipated Problem

1.0 INTRODUCTION

1.1 STUDY RATIONALE

Pain management for patients undergoing TKA is central to the successful recovery of patients from surgery. In the past, pain control has relied heavily on the use of opioid analgesics, which have resulted in serious medical and chemical-dependency problems. In an effort to reduce the use of postoperative opioid medications, multi-modal (non-opioid) analgesic techniques have emerged in recent years, including the use of peri-articular anesthetic injections. An additional technique in widespread use is the adductor canal catheter, a medical device that consists of a tunneled catheter connected to an analgesic solution-containing reservoir that slowly infuses the anesthetic over the first 2-3 postoperative days.

Despite its widespread use, the incremental benefit of the ACC beyond the other widely used analgesic methods is poorly understood. Since its use is associated with known risks (such as bleeding and patient anxiety if it falls out spontaneously) and high expense, objective data regarding the value of the ACC is urgently needed in order to make rational, evidence-based decisions about whether use of the ACC should be promoted or discouraged. To address this important evidence deficiency, The Permanente Medical Group is funding this clinical trial to better understand the proper role of the ACC in the optimal postoperative care of patients undergoing TKA.

1.2 BACKGROUND

TKA is a successful treatment option for end-stage arthritis of the knee. With an aging population and expanding indicated age-range, the annual volume of TKA surgery in the United States currently exceeds 600,000 cases and is projected to continue to increase over the next decade (1,2). Within Kaiser Permanente, we perform over 7,000 TKAs annually in Northern California alone. Published success rates following TKA surgery vary depending on the definition of success but patient satisfaction rates of at least 80% are typical (3). While causes of dissatisfaction following TKA surgery are varied, pain is the most common reported reason (4). Further, published data reported from our own institution has found that the most frequent cause of early inpatient readmission and ED visits after TKA surgery is pain (5). Pain is also one of the primary reasons patients are unable to be discharged home directly after surgery in our institution.

The last decade has seen several significant advances in the management of pain following TKA surgery. “Multi-modal anesthesia” protocols have been developed to utilize non-opioid therapies during the recovery period (6). Historically TKA patients were prescribed Patient-Controlled Analgesia machines to self-administer parenteral opioid-based pain medication. While their use enabled patients to take control of their pain medication administration, the negative impact of these parenteral opioids – including dizziness, nausea, vomiting and respiratory depression – on their recovery after surgery has been well-described (7,8).

Neuraxial and regional anesthetic techniques have been utilized in an effort to decrease reliance on opioid medications. While femoral nerve blocks were historically used in the management of post-op pain in lower extremity surgery, the block of the motor component of the femoral nerve resulted in reports of quadriceps weakness resulting in inability to work with therapy, delayed discharge to home and inadvertent falls (9,10). Adductor canal blocks (ACB) and catheters (ACC) have been described to provide a blockade to the entirely sensory saphenous nerve, as well as the vastus medialis nerve and the posterior branch of the obturator nerve without impacting the motor branches of the femoral nerve. These blocks offer an anterior and medial-based sensory blockade of the knee (11). The use of ACCs/ACBs has allowed for complete participation in post-operative rehabilitation with far fewer reports of quadriceps weakness (12). ACCs and ACBs have seen widespread adoption throughout Kaiser Permanente in the last 2 years with all but one facility in Northern California utilizing them.

In the case of an ACC, a dedicated anesthesia provider uses a portable ultrasound machine to position the catheter prior to surgery in the pre-op area or after surgery in the post-anesthesia care unit. Once the catheter is placed, it is attached to a pump and reservoir containing 450 cc of 0.2% ropivacaine solution which, when activated, releases the medication in a controlled fashion. The rate of administration can be adjusted by the patient. Currently these catheters are left in place for 3 days after surgery and are then removed by the patient at home. While the quadriceps weakness associated with

femoral nerve blocks and catheters is largely avoided in the use of adductor canal catheters, the use of ACCs is not without potential complications (13).

Another modality described for the management of post-op pain following TKA surgery has been the peri-articular injection (PAI) – an intra-operative injection into the peri-articular soft tissue of bupivacaine, epinephrine, clonidine and ketorolac (14). Its use in TKA surgery coincided with adoption of Enhanced Recovery After Surgery (ERAS) protocols in which early mobility and alternatives to opioid therapy are employed. The impact of both the PAI and ERAS protocols in TKA patients' outcomes have been well-described (15–17). PAI use in TKA surgery is now nearly universal within Kaiser Permanente and is considered one of the modalities which satisfies the ERAS metric of multi-modal pain management in elective TKA.

In 2016, CMS initiated the Comprehensive Care of Joint Replacement program to help reduce the costs associated with a total knee or hip replacement. This program shifted the reimbursement model for total hip and knee replacement surgery from one of fee-for-service to one of a single reimbursement for the entire episode of care. The introduction of this “bundled payment” reimbursement model has resulted in a renewed focus on all costs related to the total joint care pathway and has had a direct impact on the reduction of length of inpatient stay following total joint arthroplasty across the nation.

Inpatient hospital admission is one of the greatest contributors to the cost of the episode of care. In the last 7 years we have seen our length of stay for total knee replacement patients reduced from 3 days to less than one day. One of the major hurdles in safe patient discharge after TKA surgery is adequate pain control. The adoption of a multi-modal pain reduction strategy and, in particular, the use of the peri-articular injection has facilitated this reduction in LOS. Part of the rationale for the addition of adductor canal catheters to this pain-reduction strategy is to help improve post-operative pain and reduce LOS. In KPNC SLN, where we perform over 1,000 primary unilateral TKA surgeries each year, utilization of ACCs is variable among surgeons. Comparing length of stay in our primary TKA patients, we see the same rate of same day discharge among providers who use ACCs and those who do not. Further, a pilot study conducted at our facility in 2018 found only a very small (and clinically unimportant) difference in post-operative day 2 (when the effects of the PAI would be expected to have worn off) numerical pain score between patients with an ACC and those without. These findings are similar to a recently published randomized control study which found no difference in pain levels or opioid consumption between TKA patients with PAI alone or with PAI plus ACB (18). Our pilot study has also identified several complications associated with ACCs including leaking, dislodging, bleeding, hematoma development and prolonged neuropraxia, resulting in ED visits and phone calls to address these issues.

The entire cost of adductor canal catheters includes the pump, tubing and medication as well as the FTE provider who places them and the potential cost of ED visits or phone calls/office visits to address complications associated with the catheters. Given the cost of the catheters themselves (\$400) and the number of primary TKA surgeries performed annually in KPNC alone (> 7,000), the annual cost to our organization is estimated to be more than \$4 million.

Therefore, we propose this randomized, open-label, parallel-comparison noninferiority clinical trial to determine whether the effectiveness of these catheters justifies their cost.

1.3 STUDY DESIGN

This is a randomized, open-label, two-arm, parallel-comparison noninferiority clinical trial of usual care with an ACC placed preoperatively compared to usual care without an ACC among adult patients undergoing elective unilateral TKA at the KPNC San Leandro Medical Center (Figure).

All patients meeting eligibility criteria will be introduced to the study by the treating orthopedist and PI, [name], at the patient's first clinic visit. If the patient expresses interest in study participation, they will be consented over the phone by the clinic Physician's Assistant (PA). Baseline data will be obtained via a telephone call with the study Research Assistant 7-10 days prior to the date of surgery. Randomization will occur in the preoperative area immediately prior to surgery. Patients will keep a daily diary of their pain levels and analgesic medication use for two weeks postoperatively and will be called by the study Research Assistant on post-op day two and day 14. A single electronic

medical record (EMR) data extraction for adverse events (focusing on emergency department and inpatient visits) will be conducted at 30 days postoperatively.

The primary outcome is the absolute pain score on post-op day two, measured on an 11-point numerical rating scale; the noninferiority margin for this comparison is set *a priori* at 2.0 points. Secondary outcomes include the total amount of opioid consumed over the two-week post-op period, the overall pain scores over the two-week post-op period, and adverse events directly attributed to the ACC.

[figure not shown]

Figure: Study Design Schema

2.0 OBJECTIVES

2.1 PRIMARY OBJECTIVE

To compare the effect of usual care with an ACC containing ropivacaine to the effect of usual care in the absence of an ACC on the second-postoperative-day pain levels among patients undergoing elective primary unilateral TKA who receive peri-articular anesthetic injections

2.2 SECONDARY OBJECTIVES

Among a sample of patients undergoing elective primary unilateral TKA who receive peri-articular anesthetic injections:

- 1) To compare the overall two-week levels of postoperative pain between those participants randomized to ACCs containing ropivacaine and those participants randomized to usual care without an ACC
- 2) To compare the use of opioid medications (in mean total morphine milligram equivalents) between those participants randomized to ACCs containing ropivacaine and those participants randomized to usual care without an ACC over the two-week postoperative period
- 3) To estimate the incidence of complications related to ACC placement including infection, displacement, ACC-related outpatient clinic or ED visits
- 4) To conduct exploratory analyses to identify candidate predictors of differential response to the ACC; potential interacting variables for these analyses will include demographics, baseline pain NRS scores, clinical comorbidities and secondary outcome measures.

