5.1 STUDY DEVICE

The adductor canal catheter is a device which is placed by a trained anesthesia provider in order to apply analgesia to the anterior portion of the knee. It consists of a catheter, tubing and an adjustable time-release pump and reservoir. The reservoir is filled with 450 ccs of 0.2% ropivacaine. The catheter is inserted into the adductor canal, which contains the purely sensory saphenous nerve - a branch of the femoral nerve which supplies the anterior portion of the knee. The pump releases the ropivacaine in a controlled release fashion over 48-72 hours depending on the adjustable rate of the pump. When the reservoir is empty, the catheter is removed by the patient and disposed.

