5.1.3 SOURCE AND MANAGEMENT OF DEVICE

The ACC is an FDA-approved medical device in current use within KPNC. The device is considered a standard-of-care instrument and, therefore, does not require special handling for use in a research study. The ACCs used for this study will be stored in the usual hospital locations and be filled with the bupivacaine anesthetic by the hospital pharmacist, in the usual manner. The device will be placed in the legs of the intervention-allocated patients by a KPNC anesthesiologist according to usual clinical practice and it will be removed by the patient by postoperative day three, according to the manufacturer's instructions. The device will be discarded by the patient at home and not be returned for study purposes.

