6.4 DAY OF SURGERY

On the day of surgery, all preoperative activities will proceed as usual for patients undergoing TKA at the SLN Medical Center. The orthopedic surgeon, when meeting with the patient prior to surgery, will confirm once more that the patient is intending to be randomized and participate in the study. Note that there will be no additional consent procedure (as advised by the regulatory specialist with the KPNC DOR Clinical Trials Unit).

At the time when an ACC would normally be placed by the anesthesiologist (if the patient was going to have an ACC placed), the orthopedist or study PA will obtain the next consecutive randomization envelope and open it, revealing to the patient and anesthesiologist the randomization assignment. If the participant is randomized to placement of the ACC, the anesthesiologist will proceed with ACC placement as usual. If the participant is randomized to non-placement of the ACC, no ACC will be inserted and the remaining preoperative activities will continue as usual.

After surgery (whether the participant will be discharged to home on the day of surgery or admitted to the hospital), the patient will be given a packet containing all instructions for further participation, their daily pain-and-medication diary, and the closeout questionnaire). They will be told to begin filling out their diary the following day.

6.5 2-DAY FOLLOW-UP TELEPHONE CALL

On the afternoon of the second postoperative day, the study Research Assistant will call the participant at home to obtain their numerical rating pain score for the primary study outcome. They will inquire of the patient if they have any questions regarding their further participation, ensure that the participant understands their research-related responsibilities, and encourage adherence with all data

collection. Note that this call is separate from any clinical telephone calls made to the participant from the orthopedics department.

6.6 1-WEEK FOLLOW-UP TELEPHONE CALL

One week following the date of surgery, the study Research Assistant will call the participant at home to ensure that they are continuing to fill out their daily participant diary, inquire about any potential adverse events, answer any questions, and remind the patient that there will be a closeout phone call in another week.

6.7 2-WEEK CLOSEOUT TELEPHONE CALL

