Secondary Aim 1: The first secondary analysis is a comparison of the mean NRS pain scores between the two treatment groups over the two-week follow-up period. We will have up to 15 measurements per individual (daily pain scores over a two-week period including baseline measurement). We are primarily interested in whether the rate of change in NRS pain score over the two-week follow-up period differs between the two treatment groups. These analyses will be conducted with linear mixed-effects models (38,39) that include terms for the effects of time, study group and the group-by-time interaction which will serve as the primary statistical test of the study hypothesis. Subjects will be included as random effects, and the within-subject correlation will be modeled appropriately. The most appropriate error structure will be chosen by comparing model fit using Akaike's Information Criterion (40). The overall difference between two total response curves will be tested with likelihood-ratio tests. The predicted

(modeled) change in the outcome over the relevant follow-up period will be obtained from each model along with the associated standard errors from which 95% confidence intervals will be constructed.

Secondary Aim 2: The mean difference in two-week postoperative opioid use (measured in total morphine equivalents) between the two treatment groups will be compared with a two-sample t-test. A secondary analysis will be conducted with a multiple linear regression model with an indicator variable for treatment group (for which the test of $\beta_1=0$ will form the primary hypothesis test) and adjustment for baseline covariates, use of opioids at baseline, and baseline NRS pain score.

Secondary Aim 3: The frequencies of complications related to ACC will be summarized with proportions and associated exact 95% confidence intervals.

Secondary Aim 4: To identify candidate predictors of differential response to the ACC, we will consider including interaction terms between the treatment indicator and demographic variables and baseline pain NRS scores in the primary linear regression analysis.

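### Secondary Aim 1 tests a two-week pain-level objective mainly through a rate-of-change interaction and plans no contrast for the catheter period, so a short-lived ACC benefit would be diluted, missed or shown as a slower fall in pain

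*Combined protocol and SAP*

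**What the plan says.** Section 2.2 sets the first secondary objective as a question about levels: "To compare the overall two-week levels of postoperative pain between those participants randomized to ACCs containing ropivacaine" and those randomized to usual care without one.

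The treatment is short. The synopsis says "The intervention phase will occur between randomization and three days postoperatively", or until the catheter comes out. Section 5.1 (Study Device) says "The pump releases the ropivacaine in a controlled release fashion over 48-72 hours depending on the adjustable rate of the pump", and section 5.1.3 says "it will be removed by the patient by postoperative day three".

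Section 8.2, Secondary Aim 1, opens as a comparison of mean NRS over two weeks. It then says the main interest is "whether the rate of change in NRS pain score over the two-week follow-up period differs between the two treatment groups", and names the group-by-time interaction in a linear mixed model as the primary test. On the data it says "We will have up to 15 measurements per individual (daily pain scores over a two-week period including baseline measurement". Section 6.4 says of the diary "They will be told to begin filling out their diary the following day", so the postoperative scores run from day 1 to day 14. The plan adds a likelihood-ratio test of the two response curves and modelled changes with 95% intervals. It names no between-arm contrast for days 1-3 or for the days after removal.

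**The concern.** There are two separate problems.

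- **Window.** About 11 of the 14 diary days fall after the catheter is out. Even a correctly estimated two-week mean averages the treated days with a longer untreated stretch, so a benefit confined to the infusion is shrunk.
- **Test.** A rate of change is not a level. If the ACC arm starts lower and the arms then converge, the no-ACC arm has the steeper fall. A pure early benefit then appears as slower improvement with the ACC.

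The primary analysis judges one day-2 score against a 2.0-point margin. A reader looking for a smaller real benefit will turn to this secondary analysis. As planned, it could return a near-null mean or a slope pointing the other way, while the day-1 and day-3 scores already collected are never compared directly.

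**Working it through.** **Inputs from the documents.** SD 2.64, 60 evaluable per group and margin 2.0 (section 8.1); up to 15 measurements including baseline (8.2); baseline call 7-10 days before surgery (1.3).

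The plan gives no effect size or power for Secondary Aim 1. Its nearest own figure is the primary one. The z-formula 2 × [2.64 × (1.960 + 2.054) / 2.0]² gives 56.1, so 57 per group. With the stated 60, power is 98.6% against the stated 98%, so the inputs are consistent.

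**Assumptions.** The true ACC benefit is 1.0 point on days 1-3 and zero afterwards. SD is 2.64 on every day, and tests are two-sided at 5%. Six correlation structures are used: constant 0.3, 0.5 and 0.7, and a random-intercept share of 0.3, 0.5 and 0.7 plus AR(1) 0.6. For a contrast with weights w, SE = √(2 w′Vw / 60).

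**Two-week mean.** The difference is 3/14 = 0.21 points (3/15 = 0.20 if 15 days are counted). A benefit equal to the full margin gives 2.0 × 3/14 = 0.43.
- At constant correlation 0.5, SE = √(2 × 2.64² × (1 + 13 × 0.5)/14 / 60) = 0.353, z = 0.61, power 9%.
- Across the six structures SE is 0.285-0.424 and power 8-12%.

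**Days 1-3 mean.** The difference is 1.0 point.
- At constant correlation 0.5, SE = √(2 × 2.64² × (1 + 2 × 0.5)/3 / 60) = 0.394, z = 2.54, power 72%.
- Across the six structures SE is 0.352-0.458 and power 59-81%.
- If the benefit is present on only two of the three days, the contrast is 2/3 = 0.67 and power about 31-47%. If on only one day, it is 1/3 = 0.33 and power about 11-16%.

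**Slope, time linear, ACC minus no ACC.** Each value is the least-squares coefficient of the effect profile on day.
- Days 1-14: mean day 7.5, sum of squares 227.5, so the slope is 16.5/227.5 = +0.073/day, or 0.94 points over 13 days. The fitted intercept is -0.214 - 0.0725 × 7.5 = -0.76.
- Baseline at day 0 plus days 1-14: 15/280 = +0.054/day.
- Baseline at day -7 plus days 1-14: 13.6/423.7 = +0.032/day.

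These hold under constant correlation. With the intercept-plus-AR(1) structures and generalized least squares, the two baseline-included slopes fall to +0.031 and +0.016.

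| Measurements in model | Slope per day | Rejection, six structures |
|---|---|---|
| Days 1-14 only | about 0.073 | about 40-99% |
| Baseline included (day 0 or day -7) | 0.016-0.054 | about 10-92% |
| Baseline included, pure AR(1) 0.9 | 0.005-0.006 | about 5% |

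The sign was positive (slower fall with ACC) in all 32 combinations of four day grids and eight covariance settings. It was also positive when the effect lasted two days or tapered over days 4-5.

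**The case against.** Much of the case on the other side stands.

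- **The catheter period is already primary.** Day 2 lies inside the infusion, and the prompt asks about the previous 24 hours, so it is not a momentary reading. A reader might infer that the trial's main conclusion is undermined. It is not, because that conclusion does not depend on Secondary Aim 1.
- **The effect profile is assumed.** The documents give none by day. Section 1.2 expects the peri-articular injection to have worn off by day 2, which may mask day 1, and some pumps will be empty by day 3. The 59-81% is therefore a favourable case.
- **Linear time is implied, not stated.** With day as a category there is no single slope. A slower fall from a lower start is also a correct slope. A reader might infer that the plan would report catheter harm, but nothing in section 8.2 says how a slope will be interpreted.
- **The steepest slope figures leave out baseline.** A reader might take 0.073/day and 40-99% as describing the planned test. Section 8.2 counts baseline among the 15 measurements, so the lower range applies.
- **Other terms could show the benefit.** The group term carries it (intercept -0.76), and the likelihood-ratio test could detect a difference. But that test gives no direction or timing, and neither is named as the primary test of the aim.
- **A two-week summary is a legitimate pragmatic question.** It is, and it should stay. What is missing is a test that matches it and a contrast for the treated days.

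**Conclusion.** The point holds as a weakness in a secondary analysis. The objective asks about levels and the named test addresses rate of change, and no planned contrast isolates the catheter period.

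For a benefit confined to days 1-3, the two-week mean keeps about a fifth of it. With time linear, the interaction is either misleading in direction or nearly blind to the benefit, depending on the correlation structure and the placement of baseline. The dilution depends on the effect ending with the infusion, and the slope result also on linear coding of time. Neither is stated in the documents, although "slowly infuses the anesthetic over the first 2-3 postoperative days" in section 1.1 makes the first natural.

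**What to change.** In section 8.2, Secondary Aim 1, before any between-arm comparison is seen:

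1. Fit the planned mixed model with postoperative diary day as a categorical factor and baseline NRS as a covariate.
2. Make the between-arm difference in two-week mean NRS, with its 95% CI, the test of the levels objective.
3. Pre-specify two supporting contrasts with 95% CIs: mean NRS over days 1-3 and mean NRS over days 4-14.
4. State that a group-by-time slope alone will not be read as benefit or harm.

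This needs no new data, calls or participants. It costs some SAP wording and two more secondary estimates. The days 1-3 mean may itself dilute an effect confined to day 2, so it supports the day-2 primary result and does not replace it. Added after the arms have been compared, the days 1-3 contrast would be post hoc.

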2.3 PROPOSED SUBGROUPS

No subgroup analyses are proposed for this trial. As noted above (2.2, Secondary Objective #4), we will conduct exploratory analyses of potential interacting variables associated with differential (positive) response to the use of the ACC. As exploratory investigations, it is acknowledged that these analyses will likely be underpowered and are hypothesis-generating only.

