4.2 SECONDARY OUTCOMES

Originally, the secondary outcomes included the PROMIS Global Health-10 short form and the Knee injury and Osteoarthritis Outcome Score short form (KOOS Jr). However, after further reflection among the study investigators, it was decided that these measures of symptoms and functions provided little meaningful outcome data among a sample of patients soon after knee replacement. Therefore, these measures were discarded as secondary outcome measurements.

However, the investigators decided that consumption of opioid medication in the 15 days postoperatively (as provided in the postoperative pain-and-medication diary) provided an important and meaningful secondary outcome measure for assessing the analgesic effectiveness of the ACC. The main secondary outcome measure will be the total number of 5mg oxycodone tablets (provided to all patients on discharge) consumed over the 15-day postoperative period. This change is reflected in the study schema, above.

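### Secondary Objective 4 admits post-randomization secondary outcomes as effect modifiers, contrary to the baseline-only list in section 8.2; they are not valid predictors of response to the catheter

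*Combined protocol and SAP*

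**What the plan says.** Section 2.2, Secondary Objective 4, covers exploratory work on who responds differently to the catheter: "potential interacting variables for these analyses will include demographics, baseline pain NRS scores, clinical comorbidities and secondary outcome measures". The word baseline is attached only to the pain score.

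Section 8.2, Secondary Aim 4, gives the analysis: "we will consider including interaction terms between the treatment indicator and demographic variables and baseline pain NRS scores in the primary linear regression analysis". It names neither secondary outcomes nor comorbidities.

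Section 1.3 defines the secondary outcomes: "Secondary outcomes include the total amount of opioid consumed over the two-week post-op period, the overall pain scores over the two-week post-op period", together with "adverse events directly attributed to the ACC". Section 4.2 makes the main one the "total number of 5mg oxycodone tablets (provided to all patients on discharge) consumed over the 15-day postoperative period" and adopts opioid use as a way to judge how well the catheter relieves pain. On timing, section 1.3 states: "Randomization will occur in the preoperative area immediately prior to surgery".

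Section 2.3 says of the interaction work that "these analyses will likely be underpowered and are hypothesis-generating only".

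**The concern.** A predictor of differential response is useful only if it is known when the choice to place a catheter is made, and it can be studied as an effect modifier in a randomized comparison only if assignment cannot have changed it. The current secondary outcomes fail both conditions. Within levels of a variable that treatment can alter, the two arms are no longer comparable groups, so neither the treatment coefficient nor the product term has a clean reading.

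What is at stake is the candidate-predictor list. If an analyst follows 2.2, it could contain variables that reflect what the catheter did, not who benefits from it. Calling the work exploratory warns about power and multiplicity; it does not remove this bias.

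**Working it through.** The plan states no figure on this point, so the check compares sections and then uses an illustrative model.

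**1. Are the listed variables post-randomization?** Randomization is immediately before surgery (1.3). Opioid use, two-week pain and ACC-attributed events (1.3, 4.2) all accrue afterwards. So yes, for every current secondary outcome.

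**2. Consequences that need no simulation.**
- *ACC-attributed events.* Let T = 1 for the catheter arm and E = 1 for an event. Barring crossover, E = 0 whenever T = 0, so T×E = E for everyone. The product term duplicates the main effect of E and cannot be estimated.
- *Two-week pain.* The diary includes day 2, the time of the primary outcome, and section 4.1 uses that diary entry as the back-up for the primary score. The modifier would therefore partly contain the outcome.

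**3. Bias in the treatment coefficient (assumed model).** Underlying pain U ~ N(5, SD 2); day-2 score Y = U + effect×T + N(0, SD 1.7); log opioid L = 0.3(U + effect×T − 5) + N(0, SD 0.5). There is no true effect modification. The SD of Y within an arm is √(4 + 2.89) = 2.62, close to the protocol's 2.64 (8.1). The opioid relation is assumed; the documents give none.

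On the log scale the result is exact:
- slope of Y on L within an arm = 0.3×4 / (0.09×4 + 0.25) = 1.2/0.61 = 1.967
- shift in L due to the catheter at effect −1.0 = 0.3×(−1.0) = −0.3
- adjusted effect = −1.0 − 1.967×(−0.3) = −0.41

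With the untransformed total, simulation at 60 per arm gives about −0.56 without the product term, and about −0.51 with it and opioid use centred at its mean. So a true −1.0 becomes roughly −0.4 to −0.6.

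**4. False interactions (same model, two-sided 5% test of the product term).**

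| Candidate modifier | Effect −1.0 | Effect −2.0 |
|---|---|---|
| Opioid total, untransformed | about 25% | about 44% |
| Same skewed variable, not affected by the catheter | about 15% | about 15–16% |
| Opioid total, log scale | about 5% | about 5% |
| Baseline variable | about 5% | about 5% |

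At −1.0, about 15 of the 25 percentage points come from entering a skewed variable linearly. The remaining 10 or so come from the catheter's effect on that variable.

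**5. A second assumed model.** SD 2.64, 60 per arm, no true modification:
- Opioid use as a skewed count, pain bounded at 0–10: 11%, 17% and 28% false interactions for catheter benefits of 0, 1 and 2 points. If the catheter also lowers opioid use directly: 38%, 57% and 71%.
- Linear normal version: 4.6% to 5.3%, so no excess. The coefficient is still biased: a true −1.0 becomes −0.59, or +0.21 with a direct effect on opioid use.
- Baseline modifier: 4.0% to 5.4% throughout.

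**6. The two lists side by side.** Section 2.2: demographics, baseline pain, comorbidities, secondary outcomes. Section 8.2: demographics, baseline pain. They differ on two items, and 8.2 does not say that the other two are excluded.

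**The case against.** The strongest reply is that section 8.2 is the operative plan. Followed as written, it fits no treatment-by-outcome interaction, and the synopsis version of Objective 4 lists no interacting variables at all. This stands in part. A reader might infer that the trial is committed to these interactions, and the documents do not support that: the defect is a phrase in the objectives that 8.2 does not carry. But 2.2 says what the variables will include, while 8.2 only says terms will be considered, so an analyst could follow either.

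Second, the phrase may be a leftover. Section 4.2 says the secondary outcomes once were PROMIS Global Health-10 and KOOS Jr, and Appendix 1 still schedules both at the preoperative call. Their baseline values would be legitimate modifiers. This reading is plausible but unproved: the text does not say baseline, and 4.2 has dropped both instruments as secondary outcomes.

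Third, post-randomization status does not by itself create false interactions; on the log scale or in a linear normal model the test keeps its level. This stands, so false predictors can arise but are not inevitable. The documents do, however, plan opioid use as tablets or total morphine equivalents and mention no transformation, and the bias in the treatment coefficient remains either way.

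Fourth, section 2.3 already limits the work to hypothesis generation. That limits the consequence, not the bias.

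**Conclusion.** The concern holds as a fault in the wording of section 2.2 and an unreconciled conflict with section 8.2. Under the current definitions, secondary outcomes are not valid predictors of response. That conclusion, the non-estimable interaction for ACC-attributed events (barring crossover) and the overlap of two-week pain with the primary outcome rest on the documents' own definitions.

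The sizes are illustrative. They rest on an assumed opioid-pain relation, assumed catheter effects of 0 to 2 points and 60 per arm. Bias in the conditional treatment coefficient appears in every version in which the catheter changes opioid use; excess false interactions depend on skewness and on the scale used.

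A reader might go further and infer that the primary result is compromised. It is not: the noninferiority test in 8.2 comes from a model of day-2 pain on treatment and covariates poorly balanced at baseline, without these terms. The sample size and the planned comparisons of pain and opioid use do not depend on this aim either. The point is worth correcting because the correction is nearly free, not because a main conclusion depends on it.

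**What to change.** In section 2.2, Secondary Objective 4, delete the last item in the list of interacting variables. Alternatively, state that only values measured before randomization will be used; this would keep baseline PROMIS-10 and KOOS Jr available if they were in fact collected.

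Then put one identical list of pre-randomization modifiers in 2.2 and in 8.2, Secondary Aim 4: demographics, baseline pain score and, if wanted, comorbidities and baseline opioid use. Section 8.2 already uses baseline opioid use as a covariate for Secondary Aim 2, and section 4.3 already collects prior medication use and comorbidities. State in 8.2 that the list is closed.

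The cost is wording only: no new data, no change to sample size and no change to the primary analysis.
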